#### **D. RESEARCH DESIGN AND METHODS AND DATA ANALYSIS**

**Research Design.** We will invite 56 women with an APO within the past 3 yrs to participate. Women will be randomly assigned to the 4-wk intervention group (n=28) or a standard care group (n=28) using a computerized random number generator, stratified by race. Assuming up to 25% with poor adherence, we expect that 42 women (21 each arm) will complete the study. No data exists related to effects of supplementation on vascular function in our population, we assumed a medium effect size, i.e. Cohen's  $d \sim 0.50$  and accepting a  $\beta=0.80$ , to generate sample sizes. Generation of effect sizes is a key outcome of this study. We will conduct a vascular assessment and blood draw at two visits: before the intervention begins and within 3 days of completing the intervention. We will conduct visits during the early follicular phase of menstrual cycle to account for fluctuating hormones. Vascular testing will be performed in the supine position and  $\geq 4$  hours after a light meal. Surveys for Aim 2 will be completed within the first 2 weeks of study enrollment, and interviews for Aim 2 will be conducted within 1 week of Visit 2, in-person or via telephone.

**Anti-inflammatory supplementation intervention.** Participants randomized to the supplementation intervention will receive PolyResveratrol-SR® (100 mg curcumin phytosome, 100 mg quercetin phytosome, 100 mg green tea phytosome, 100 mg trans-resveratrol, 100 mg trans-pterostilbene; Thorne Research). Participants will be asked to take 2 doses/day (1g total). Participants randomized to supplementation will receive a daily email reminding them to take the supplement. **Covariates.** Medical history, age, and sociodemographics will be obtained via self-report. We will use validated surveys to determine physical activity, sedentary behavior, and smoking history. Height and weight will be measured.

**Aim 1 Outcomes.** The outcomes will be measured in-person. All outcomes are listed and described below. [name] has extensive experience collecting the measurements described below.

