6. *Blood analyses*. We will collect 30 mL(2 Tb) of blood into an EDTA containing tube and serum tube using venipuncture and a butterfly needle. Blood will be centrifuged at 1300 g for 10 min, aliquoted into 0.25 mL cryotubes, and stored at -80°C until analysis. We will determine levels of circulating IL-6, IL-10, ICAM-1, and VCAM-1 using commercially available ELISA kits (R&D Systems). We will bank unusedl blood for future, as yet undetermined analyses. Participants will be informed of this intent before providing blood. Blood will be labelled and linked to clinical data and demographics using a

unique identifier; samples will be de-identified for storage at the PHRC and for future analyses.

7. **Covariates: Medical and Pregnancy History and Demographics.** We will ask questions about demographic, medical, and pregnancy history. Answering questions will not provide identifiable information, **Self-reported activity:** We will use validated surveys to quantify physical activity and sedentary behavior, **Diet History.** We will use a validated survey to assess diet composition in the previous 6 months.

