**Data Analyses.** We will calculate the 25th and 75th percentile for each biomarker and vascular function test and use these values as cut-offs for “low” and “high” levels, respectively. We will test for differences in biomarker levels between women by APO status and race using a t-test or Mann-Whitney U test, depending on the distribution of the variables. We will use separate multiple linear regression models to determine associations of each exposure (continuous levels of biomarkers; quartiles; and high or low levels of these biomarkers) with continuous measures of our outcomes (individual indices of vascular function, e.g. BP, arterial stiffness, augmentation index, FBF, endothelial function, and intima-media thickness) in all 56 women. We will use logistic regression to test for associations between continuous and categorical levels of biomarkers with categorical outcomes: the likelihood of having hypertension or prehypertension, high central arterial stiffness, low endothelial function, and high carotid intima-media thickness in all 56 women. We will test for unadjusted associations and then adjust all regression analyses for key co-variables: maternal age, race, and smoking. We will test for associations after furthering adjusting for years of education, body mass index (BMI), parity, and physical activity, in the index pregnancy in exploratory analyses. We will test for an interactive effect of APO status and race on these associations using a multiplicative interaction term in separate analyses and conduct all analyses stratified by APO status and/or race if the interaction is significant. We will conduct a sensitivity analysis by repeating our statistical tests only in the primiparous women as prior pregnancy is associated with lasting changes in vascular function and may influence our outcome and exposure variables.

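### Race-specific biomarker-vascular associations are to be run only after a significant interaction test, which makes their display selective and leaves a silent test uninformative in 56 women

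*Combined protocol and SAP*

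**What the plan says.** The rule is in Section D, Data Analyses. The regressions are described as follows: "We will use separate multiple linear regression models to determine associations of each exposure". The exposures are the biomarkers, in several forms: "continuous levels of biomarkers; quartiles; and high or low levels of these biomarkers". The outcomes are "individual indices of vascular function, e.g. BP, arterial stiffness, augmentation index, FBF, endothelial function, and intima-media thickness", and the models are to be fitted in all 56 women. Logistic models for categorical outcomes follow. All regressions are adjusted for age, race and smoking.

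The interaction step reads "We will test for an interactive effect of APO status and race on these associations using a multiplicative interaction term in separate analyses", and the same sentence continues that the team will "conduct all analyses stratified by APO status and/or race if the interaction is significant".

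The four biomarkers are named in Section D, Aim 1 Outcomes, item 6: "We will determine levels of circulating IL-6, IL-10, ICAM-1, and VCAM-1".

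The plan gives no significance level, no count of interaction tests, no multiplicity rule, no power for the interaction and no interval to accompany it. It does not say which significant interaction causes which analyses to be stratified. Randomisation is stratified by race (Section D, Research Design), but no expected race split is given for the 56 women.

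**The concern.** Whether a race-specific association is estimated depends on a p-value, and that p-value is examined in many separate models. Two problems follow, and they must be kept apart.

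- **Across the set of models**, some interaction is likely to reach significance by chance even if race modifies nothing. The stratified results that follow are selected because the observed slopes differed, so the differences shown will tend to be too large.
- **In any one model**, 56 women give little power to detect an interaction. When the test is not significant, the plan calls for no race-specific estimate, and the reader sees only a pooled slope. The reader then cannot tell that the data were also compatible with a large difference.

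At stake is the reading of the biomarker-vascular associations by race. Section C says that race was the one factor linked to preterm or small-for-gestational-age delivery in the team's earlier work, so readers will probably look at this.

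**Working it through.** **Plan's own figure.** There is none for this test. The sample-size statement in Section D (Cohen's d about 0.50) is not about an interaction.

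**Inputs**

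- N = 56 (Section D, Data Analyses).
- 4 biomarkers (Aim 1 Outcomes, item 6) and 6 vascular indices named as examples in Data Analyses. This gives 4 x 6 = 24 continuous linear models, each with one biomarker-by-race term.
- Two-sided alpha 0.05: assumed, not stated.
- Race split: assumed. The Section C table gives 28% and 17% African American in its two columns. 0.28 x 56 = 15.7, so 16/40. 0.17 x 56 = 9.5, so 10/46. An even 28/28 split is the favourable end.
- Correlation among biomarkers and among outcomes: assumed, 0 to 0.7.
- True difference when there is one: 0.5 residual SD of outcome per SD of biomarker, assumed.

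**1. False firing anywhere among the 24 tests.** Expected false positives are 24 x 0.05 = 1.2. If the tests were independent, P(at least one) = 1 - 0.95^24 = 0.708. Simulated results (3,000 trials per setting; model with biomarker, race, their product and age) are:

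| Correlation | 16/40 split | 28/28 split |
|---|---|---|
| 0 | 71% | 71% |
| 0.2 | 67% | 68% |
| 0.3 | 65% | 64% |
| 0.5 | 54% | 54% |
| 0.7 | 38% | 37% |

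The false-positive rate per test stayed at about 5% throughout. Adding exposure codings at a 16/40 split and correlations of 0.5 to 0.3 raised the family rate to 76-86% with three codings (72 tests) and 87-93% with four (96 tests). The logistic models were not simulated and would add more tests.

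**2. Missing a true difference in one specified model.** With random biomarker values, the standard error of the slope difference in SD units is about sqrt(1/(n1-3) + 1/(n2-3)). The 95% half-width is 1.96 x SE, and approximate power is Phi(0.5/SE - 1.96).

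| Split | SE | 95% half-width | Approximate power | Miss rate, formula | Miss rate, simulated |
|---|---|---|---|---|---|
| 28/28 | sqrt(2/25) = 0.283 | 0.55 | 42% | 58% | 58% |
| 16/40 | sqrt(1/13 + 1/37) = 0.322 | 0.63 | 34% | 66% | 65% |
| 10/46 | sqrt(1/7 + 1/43) = 0.408 | 0.80 | 23% | 77% | 75% |

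Treating the biomarker values as fixed gives somewhat lower miss rates, 54-72%.

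**3. What selection does to the estimate.** To be significant, an observed slope difference must exceed roughly the half-width, 0.55-0.80 SD. A true difference of 0.5 SD therefore typically reaches the stratified tables only when it has been overestimated.

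**4. Like-for-like comparison.** For a single test, the rates are 5% false firing and 58-75% missed. For the family of 24 with one true 0.5-SD difference, the chance that nothing fires at all is about 19-34% (correlations 0 to 0.5, all three splits). That is much lower than the single-test miss rate, but some of those firings are in other models than the one with the true difference.

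**The case against.** The strongest reply is that this is a secondary, observational analysis inside a pilot, and that no stated conclusion of the trial depends on it. That stands and limits the importance of the point.

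Several stronger readings are tempting, and the documents do not support them:

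- **One rule with both error rates at once.** A reader might set 54-71% beside 58-75% as if they described the same decision. The first is for any of 24 tests; the second is for one specified test. Step 4 gives the proper comparison.
- **All race results are gated.** They are not. Data Analyses compares biomarker levels by race without any condition, and every regression is adjusted for race. The gate covers only the biomarker-vascular associations and does not touch the supplement effect or adherence.
- **The plan treats non-significance as proof of sameness.** It never says so. The pooled models are planned unconditionally ("intima-media thickness) in all 56 women"). The weakness is only that nothing else is called for when the test is silent.
- **Stratified results will be mostly chance findings.** That would require true interactions to be rare, which nobody has shown. What can be said is that selection favours large observed differences.
- **Race matters here because it is the randomisation stratum.** Stratified randomisation has no bearing on associations that are not randomised. The association with race reported in Section C concerns delivery outcomes, not biomarker-vascular slopes.

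The interaction sentence is also ambiguous. It could mean a term involving APO status, but that does not vary in this sample. Biomarker by race is the reading that can be carried out, and the figures rest on it. Finally, the race anchor is soft: 28% is not a whole number of women out of 17 (4/17 = 23.5%, 5/17 = 29.4%). It is used only to choose a range.

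**Conclusion.** The point holds for the race-stratified biomarker-vascular associations, with minor to moderate importance. Showing race-specific estimates only after a significant interaction makes their display depend on a large observed difference. With no true difference, something would fire in the 24 continuous models about 54-71% of the time at correlations of 0.5 to 0, just under 40% at 0.7, and more often once the other codings and the logistic models are counted. Taken on its own, a given test would miss a 0.5-SD slope difference about 58-75% of the time, and its 95% interval would reach about 0.55-0.80 SD either side of the estimate. A non-significant result could not exclude a large difference.

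These figures assume biomarker-by-race terms, two-sided 0.05, standard normal measures with equal pairwise correlations, and race splits from 28/28 to 10/46. None of the ranges is a bound. That the rule is selective, and that a silent test is uninformative, does not depend on the exact values.

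**What to change.** In Section D, Data Analyses, drop the significance trigger for race and replace it with a fixed reporting rule:

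- For each continuous biomarker-outcome linear model, report the biomarker-by-race interaction estimate with its 95% CI and the two race-specific slopes from that same model, whatever the p-value.
- Label these exploratory and state the number of interaction tests (24 if the six named indices are used), because about 1.2 intervals would still exclude zero by chance.
- Keep the already planned pooled, race-adjusted model in all 56 women as the main result.
- Do not rerun the quartile, high/low or logistic analyses in race subsets on the strength of a p-value.
- State that a non-significant interaction does not show that the associations are alike across race.
- Say explicitly that the interaction is biomarker by race, and remove APO status as a modifier since it does not vary.

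The cost is a few sentences and one exploratory table (24 interaction estimates and 48 slopes) from models already planned, with no new data or participants. The downside is that many of the intervals will be wide. That is an honest picture of what 56 women can show, and it suits a pilot that counts generating effect sizes among its key outcomes.

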#### **Aim 2 Outcomes:**

1. **Acceptability of Dietary Supplementation.** We will administer surveys to all participants to understand their perceptions of dietary supplementation, including potential benefits and consequences associated with supplementation. We will determine willingness to use supplements, barriers to supplementation, and who, i.e., physician or partner, influences their decision to use dietary supplements.
2. **Adherence and Barriers to Adherence.** We will count pills to determine adherence to supplementation regime. We will assess each intervention participant’s perceptions of supplementation with a brief interview at the final visit. Interviews will capture participant’s perceptions of the role of supplementation for CVD prevention, and any side effects of supplementation. We will ask participants to recommend ways to encourage participation and ask questions regarding their perceptions of the incentive structure and contact with the study team. We will contact participants who drop out of the study to identify reasons for drop out.

**Statistical analyses:** Acceptability survey data will be collected using a Likert Scale, tallied and averaged. We will determine the proportion of participants with adequate adherence ( $\geq 80\%$ ) to supplementation. If  $\geq 80\%$  of women have adequate adherence, we will conclude acceptable adherence is feasible with the existing incentive structure. Analysis of all post-intervention interview data will use an inductive approach and systematically guided by the constant

comparison technique. Qualitative data analysis software (QRS NVivo 10) will be used to code data and organize the analysis.

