## **A. SPECIFIC AIMS**

- 1. Aim 1. Determine the effects of a 4-week course of anti-inflammatory supplementation (PolyResveratrol-SR®) on vascular function, subclinical atherosclerosis and CV biomarkers**
- 2. Aim 2. Define adherence and barriers to compliance to supplementation.**

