## **B. BACKGROUND AND SIGNIFICANCE**

Adverse pregnancy outcomes (APOs) occur in up to 20% of all pregnancies and are associated with a lifetime of higher cardiovascular disease (CVD) risk. **Aberrant and persistent systemic inflammation is a hallmark of both APOs and CVD.** An inappropriate uterine innate immune response to invading fetal cytotrophoblasts is thought to underlie poor placentation and vascular-related APOs; inflammation of the uterine cavity evokes contractions and contributes to preterm birth. Levels of cytokines involved in endothelial inflammation, an instigating event in hypertensive and atherosclerotic processes, were higher in the 2nd trimester in women destined to have APOs. Women with a past APO have higher levels of systemic inflammation, including c-reactive protein and interleukin-6 (IL-6), in the years after delivery versus women with no APOs. A similar pro-inflammatory cytokine profile has been observed in patients with overt CVD. **Intervening on systemic inflammation may be a viable strategy to interrupt the progression from APO to CVD.**

Dietary supplements, such as polyphenols, are anti-inflammatory and inhibit vascular inflammation with potentially few barriers to adherence. **Given the hypothesized contribution of a persistent pro-inflammatory state to the excess CVD risk observed in women after APO, utilization of a polyphenol dietary supplement to specifically target inflammation holds promise as a low-burden intervention to prevent or delay APO-related CVD.** To our knowledge, efficacy and tolerability of a dietary polyphenol supplement has not been investigated in women with a history of APO. To fill in this critical gap in knowledge, we propose to test the vascular function and CV biomarker, i.e., IL-6, IL-10, intracellular and vascular cell adhesion molecule-1 (ICAM-1 and VCAM-1), responses to a 4-week anti-inflammatory dietary supplementation in a clinical trial pilot study of 56 women, 28 assigned to the intervention and 28 to the control group, in the first 3 years after an APO.

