### **5. POTENTIAL RISKS:**

The risks of the proposed studies are minimal. The main risks are (1) minor discomfort or bruising during phlebotomy and plethysmography; (2) unforeseen side effects of supplementation; and (3) loss of confidentiality. We will minimize risks 1 and 3 with standardized training of all study staff and by using HIPAA-compliant databases. Participants will be seated during the blood draw, and juice and snacks provided if needed. A maximum of three needle sticks will be permitted. Given that the supplement for the study is readily available over the counter and we're screening for known sensitivity, we do not anticipate severe side effects. We

will inform participants of the supplement ingredients during screening and in the Informed Consent document and exclude individuals with known sensitivity to the ingredients.

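### Experienced side effects are asked only of supplement women, once after the intervention, so their frequency cannot be set against a background symptom rate

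*Combined protocol and SAP*

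**What the plan says.** - **Rationale (section B).** The background states that "efficacy and tolerability of a dietary polyphenol supplement has not been investigated in women with a history of APO". The next sentence proposes the trial to fill that gap, and names vascular function and biomarker responses as what will be tested.
- **Aim (section A).** The nearest formal aim is Aim 2: "Define adherence and barriers to compliance to supplementation". Tolerability is not a named aim or endpoint.
- **Who is asked about side effects (Aim 2 Outcomes, item 2).** "We will assess each intervention participant’s perceptions of supplementation with a brief interview at the final visit". One topic of that interview is "any side effects of supplementation". No symptom list, severity grade or recall period is given.
- **When.** Item 2 places the interview at the final visit, whereas the Research Design paragraph of section D says "interviews for Aim 2 will be conducted within 1 week of Visit 2, in-person or via telephone". Either way it is a single contact.
- **Analysis.** "Analysis of all post-intervention interview data will use an inductive approach". No count, proportion or comparison between arms is planned for side effects.
- **What both arms receive (Aim 2 Outcomes, item 1).** "We will administer surveys to all participants to understand their perceptions of dietary supplementation". Section D times this survey in the first 2 weeks after enrolment. Its topics are expected benefits and consequences, willingness, barriers and who influences the decision. Symptoms experienced are not among them.
- **Dropouts.** Participants who leave, with no restriction by arm, are contacted for their reasons.
- **Risks (section E.5).** "unforeseen side effects of supplementation" is one of three main risks. The plan responds with screening and exclusion for known sensitivity and with disclosure of ingredients. It describes no collection of adverse events during the trial in either arm.

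**The concern.** Some women will have symptoms in any 4-week period, whether or not they take a supplement. A frequency of side effects in the supplement arm becomes informative about the supplement only when set against what the same women reported beforehand, or against what comparable women report without it. The plan collects neither. The interview topic is also framed as effects of supplementation, so each woman has to judge the cause for herself before she mentions a symptom.

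At stake is what the pilot can say about tolerability, which its own background cites as unknown. The same count in the supplement arm could reflect an excess or no excess, and the data would not tell the two apart. A randomised standard-care arm already exists, and the two study visits are not limited to one arm. The missing answers would be cheap to collect during the trial and could not be reliably recovered afterwards.

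**Working it through.** **Inputs from the documents.** Section D gives 28 women per arm, up to 25% lost to poor adherence, and 21 per arm completing. The retention arithmetic reproduces: 28 × 0.75 = 21 per arm and 56 × 0.75 = 42 in total. The documents state no figure for side effects or tolerability.

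**Assumption.** The documents give no background symptom rate. I use a range of p = 10% to 30% for any given symptom over 4 weeks.

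**Step 1: reports expected with no supplement effect.** This is n × p.
- n = 21: 21 × 0.10 = 2.1 and 21 × 0.30 = 6.3, so about 2 to 6 women.
- n = 28: 28 × 0.10 = 2.8 and 28 × 0.30 = 8.4, so about 3 to 8 women.

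**Step 2: what supplement-arm data alone can show.** Suppose 6 of 28 women report a symptom: 6/28 = 21.4%, exact 95% CI 8.3% to 41.0%. The excess is 21.4 − 10 = +11.4 points if background is 10%, and 21.4 − 30 = −8.6 points if it is 30%. With 6 of 21 the proportion is 28.6% (exact 95% CI 11.3% to 52.2%) and the excess is +18.6 or −1.4 points. The sign depends on a background rate that the trial does not measure. Supplement-arm counts could still bound the absolute rate: with no events, the one-sided 95% upper limit is 1 − 0.05^(1/n), which is 13.3% for n = 21 and 10.1% for n = 28.

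**Step 3: precision if both arms are asked.** With the same rate p in both arms, the 95% half-width of the risk difference is 1.96 × √(2p(1 − p)/n).
- n = 21, p = 0.10: 1.96 × √(0.18/21) = 0.181.
- n = 21, p = 0.30: 1.96 × √(0.42/21) = 0.277.
- n = 28, p = 0.10: 1.96 × √(0.18/28) = 0.157.
- n = 28, p = 0.30: 1.96 × √(0.42/28) = 0.240.

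So the half-width is about 18 to 28 points at the expected completers, and 16 to 24 points if everyone responds.

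**Step 4: how large an excess could be detected.** This uses the normal approximation for two proportions, two-sided 5%, with pooled variance under the null. Power = Φ{(d − 1.96 × √(2p̄(1 − p̄)/n)) / √([p₀(1 − p₀) + p₁(1 − p₁)]/n)}, where d = p₁ − p₀ and p̄ is their mean. Take 20% against 40% as an illustration:
- n = 21: (0.200 − 0.277)/0.138 = −0.56, power 0.29.
- n = 28: (0.200 − 0.240)/0.120 = −0.335, power 0.37.

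Solving for 80% power over background rates of 10% to 30% gives a detectable excess of 38.5 to 42.5 points at 21 per arm, and 32.5 to 37 points at 28 per arm.

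**The case against.** The strongest reply is that tolerability is background wording and not an objective. Aim 2 concerns adherence and barriers. For that purpose, side effects as the woman perceives them are the relevant quantity, and no control group is needed to learn that they put her off the pills. Pill counts, interviews and dropout reasons serve the aim as written. This stands: the point is a gap between rationale and data collection, and a reader who inferred a failed endpoint would go beyond the documents.

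Three further inferences are tempting but unsupported.
- A reader might infer that the side-effect risk has no mitigation, because section E.5 ties staff training and databases to the other two risks. The same section goes on to screen for sensitivity and disclose ingredients, and section E.1 excludes women with known sensitivity. What the text does not describe is ascertainment during the trial.
- A reader might infer that the plan will attribute every reported symptom to the supplement. It says nothing of the kind. It plans qualitative coding of perceptions and no causal or incidence statement.
- A reader might infer that the interview is the sole route by which intolerance could surface. Dropouts are also asked why they left. That yields reasons and no background rate, and section E.9, which ends data collection at withdrawal, leaves its reach unclear. The consent pages are not available, so any reporting instructions there cannot be checked.

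A second reply is that the trial is too small for a comparison to help. Step 4 shows this is right for testing, and it limits the remedy to description. It does not remove the case for it: section D makes generating effect sizes a key outcome, and an interval around a difference between arms fits that purpose. A third reply, that women who know they take a supplement may report more, also stands. A common checklist does not cure that.

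**Conclusion.** The point holds as a cheap improvement to a pilot. In the visible text, experienced side effects are asked only of supplement women, in one brief post-intervention interview without a stated symptom list. No symptom question is planned for standard-care women or at baseline. Any symptom frequency in the supplement arm therefore cannot be compared with background.

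The gain from asking both arms is descriptive. The precision in step 3 rests on the assumed 10% to 30% background rate and on a normal approximation that is rough at these counts. Modest excesses would remain undetected, and any difference seen would be open to reporting bias because no placebo is described. Aim 1 and the adherence part of Aim 2 are unaffected.

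**What to change.** - Give every woman in both arms the same short, fixed symptom checklist (yes/no and severity) at Visit 1 and Visit 2. Use neutral wording that does not ask whether the supplement was the cause, and state the recall period.
- Report counts by arm at each visit and the Visit 2 risk difference with its 95% CI. Label these results descriptive and state how many women answered in each arm.
- Keep the interview with supplement women as qualitative data on perceptions and barriers, and report dropout reasons by arm alongside.
- State as a limitation that reporting may differ between arms because no placebo is described.
- Reconcile the two statements of interview timing in section D (at the final visit, or within 1 week of Visit 2).

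The cost is one form and a few minutes at two visits that already take place. No change to sample size or visit schedule is needed.
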